#### 4.5.3.6 Management of Non-Hematologic NCI-CTCAE grade 3 or 4 AZD2281 Treatment Related Adverse Events

Treatment with AZD2281 must be interrupted for any non-hematologic CTCAE grade 3 or 4 adverse event which the Investigator considers to be related to administration of AZD2281. Repeated dose interruptions of up to a maximum of 28 days are allowed. Patients whose NCI CTCAE grade 3 or 4 event does not resolve to  $\leq$  grade 1 or to the baseline CTCAE grade after a full 28 day dose interruption should be withdrawn from the study.

Upon appropriate resolution of the toxicity (i.e., to NCI CTCAE grade 1 or to baseline CTCAE grade), the patient should restart treatment with AZD2281 but with a 50% dose reduction (as per [Table 7](#)). The dose of AZD2281 should not be reduced to less than 50 mg bid daily for patients receiving continuous AZD2281 dosing or to less than 50 mg bd for days 1-3 of a 21 day cycle for patients receiving intermittent AZD2281 dosing.

If the event recurs with the same severity, treatment should be interrupted again and, on resolution, a further dose reduction made where allowed.

Once a chemotherapy combination dose is reduced due to toxicity, combined chemotherapy dose re-escalation is not permitted.

**Table 7 Management of Non-Hematologica Grade 3 and 4 AZD2281 Treatment Related Adverse Events whilst the patient is receiving combination therapy**

Initial Dose Level c	1 st Event Occurrence - Recommended Dose Reduction	2 nd Event Occurrence – Recommended Dose Reduction	Dose Administration
100 mg bid	50 mg bid	No reduction allowed – withdraw patient	Continuous
200 mg bid	100 mg bid	50 mg bid	Continuous
400 b mg bid	200 mg bid	100 mg bid	Continuous
50 mg bid	No reduction allowed – withdraw patient	Not applicable	Continuous

**Table 7 Management of Non-Hematologica Grade 3 and 4 AZD2281 Treatment Related Adverse Events whilst the patient is receiving combination therapy**

Initial Dose Levelc	1st Event Occurrence - Recommended Dose Reduction	2nd Event Occurrence – Recommended Dose Reduction	Dose Administration
100 mg bid days 1-10 of a 21 day cycle	100 mg bid days 1-5 of a 21 day cycle	100 mg bid days 1-3 of a 21 day cycle	Intermittent
50 mg bid days 1-5 of a 21 day cycle	50 mg bid days 1-3 of a 21 day cycle	50 mg bid days 1-3 of a 21 day cycle Reduce cisplatin to 60 mg/m 	Intermittent
50 mg bid <5 days dosing of a 21 day cycle	50 mg bid days 1-3 of a 21 day cycle Reduce cisplatin to 60 mg/m 	No reduction allowed – withdraw patient	Intermittent
50 mg bid days 1-5 dosing of a 21 day cycle with cisplatin dosed at 60 mg/m 	50 mg bid days 1-3 of a 21 day cycle Cisplatin dose to remain at 60 mg/m 	50 mg bid days 1-3 of a 21 day cycle Reduce cisplatin to 50 mg/m 	Intermittent
Dose schedule advised by safety monitoring committee	Patients on other dose schedules should have their dose decreased as appropriate in line with the above guidance		

a With the exception of grade 3 or worse neurologic toxicity, in which case both cisplatin and AZD2281 should be discontinued, as per Section 4.5.3.8

b If 400 mg bid dose is explored

c Initial dose level includes cisplatin dosed at 75mg/m^2 unless stated otherwise

**Note:** The patient must be withdrawn if there is a third occurrence of any non-haematologic Grade 3 or 4 AZD2281 Treatment Related Adverse Events.

**4.5.3.7 Management of Non-Hematologic NCI-CTCAE grade ≤2 AZD2281 Treatment Related Adverse Events whilst the patient is receiving combination therapy**

For non-hematologic toxicities of CTCAE grade ≤2 that the investigator feels are related to the administration of AZD2281, the investigators should use their discretion in deciding whether dose interruptions are necessary and should also treat the events as medically appropriate based on signs and symptoms.

Except as noted above, the dose of AZD2281 must not be modified under any other circumstances unless prior agreement is given by AstraZeneca Pharmaceuticals.

*Management of new or worsening pulmonary symptoms:* If new or worsening pulmonary symptoms (e.g. dyspnoea) or radiological abnormality occurs, an interruption in AZD2281 dosing is recommended and a diagnostic workup (including a high resolution CT scan) should be performed, to exclude pneumonitis. Following investigation, if no evidence of abnormality is observed on CT imaging and symptoms resolve, then AZD2281 treatment can be restarted, if deemed appropriate by the investigator. If significant pulmonary abnormalities are identified, these need to be discussed with the AstraZeneca Study Physician.

All dose reductions and/or interruptions (including any missed doses), and the reasons for the reductions and/or interruptions are to be recorded in the CRF.

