#### 4.4.6 Discontinuation of Study Treatment

##### 4.4.6.1 Criteria for Discontinuation from Study Treatment

Patients may be discontinued from investigational product (IP) in the following situations:

- Patient decision. The patient is at any time free to discontinue treatment, without prejudice to further treatment

- Adverse event
- Severe non-compliance to study protocol
- Any CTCAE grade 3 or 4 events that have not reverted to CTCAE grade 1 or less within 28-days. At the Investigator's discretion, following dose interruption, patients may be considered for dose reductions. However, if upon re-challenging with AZD2281 at the lowest reduced dose, (for guidelines refer to Section 4.5.3), any CTCAE grade 3 or 4 adverse events recur, the patient must be discontinued.
- Bone marrow findings consistent with myelodysplastic syndrome/acute myeloid leukaemia
- Disease progression

Note: Patients may continue to receive study treatment following objective progression provided that, in the opinion of the Investigator, the patient is benefiting from the treatment and does not meet any other discontinuation criteria.

In the event that cisplatin is permanently discontinued on the basis of cisplatin related toxicity, treatment with AZD2281 alone may continue. If the patient does continue on AZD2281 alone, at the discretion of the PI and in consultation with AstraZeneca Study Team Physician, the patient may be dose escalated to receive the optimal monotherapy dose (i.e.: 400 mg bid).

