Other clinically significant grade $\geq 3$ toxicities	Hold up to 28 days until recovery to $\leq$ grade 1 or baseline if considered possibly related; reduce dose as per Table 7. After resumption, if toxicity returns interrupt. If toxicity does not recover to $\leq$ grade 1, discontinue AZD2281. The minimum dose of AZD2281 is 50 mg bid days 1-3 of a 21 day cycle for patients treated with intermittent dosing and 50 mg bid for patients treated with continuous dosing.	Hold up to 14 days until recovery to $\leq$ grade 1 or baseline if considered possibly related; may resume at current dose or with dose reduction, to a minimum of 60 mg/m  , per the Investigator’s discretion
Grade 4 non-hematologic toxicities attributable to cisplatin	No change unless cisplatin is discontinued. If cisplatin is discontinued, at the investigators discretion and if treatment criteria are met, dose of AZD2281 can be escalated to 400 mg bid continuously.	Discontinue cisplatin. If the investigator believes that the patient is benefiting from combination therapy then reducing cisplatin to 50 mg/m  and maintaining the dose of AZD2281 may be considered instead of the above after discussion with the Principal Investigator and agreed by AstraZeneca.

a The dose reductions advised in the table relate to patients who had an initial cisplatin dose of 75mg/m^2, for those patients that had their initial cisplatin dose administered at 60 mg/m^2, the dose modification of cisplatin should be a reduction to 50 mg/m^2 per the Investigator’s discretion.

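### At the AZD2281 minimum dose, 4.4.6.1 read literally stops a patient whom the 50 mg bid days 1-5 rows of Tables 6 and 7 restart with less cisplatin

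*Protocol*

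**What the plan says.** Protocol 4.4.6.1 sets a stopping rule for re-challenge. Its condition is "if upon re-challenging with AZD2281 at the lowest reduced dose", followed by a pointer to Section 4.5.3 for guidance. Its consequence is that if "any CTCAE grade 3 or 4 adverse events recur, the patient must be discontinued".

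The lowest intermittent dose is stated twice, neither time with reference to cisplatin. Section 4.5.3.6 says that AZD2281 should not be reduced below 50 mg bid in continuous dosing "or to less than 50 mg bd for days 1-3 of a 21 day cycle" in intermittent dosing. Table 8, in 4.5.3.8, says: "The minimum dose of AZD2281 is 50 mg bid days 1-3 of a 21 day cycle for patients treated with intermittent dosing".

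Tables 6 (haematologic) and 7 (non-haematologic) each have two rows for a start at 50 mg bid days 1-5, one with cisplatin 75 mg/m² and one with 60 mg/m². In both rows the first event brings AZD2281 to 50 mg bid days 1-3. The second-event cell for the cisplatin 75 row is "50 mg bid days 1-3 of a 21 day cycle Reduce cisplatin to 60" mg/m², and for the cisplatin 60 row "50 mg bid days 1-3 of a 21 day cycle Reduce cisplatin to 50" mg/m². The note under Table 7 reads "The patient must be withdrawn if there is a third occurrence of any non-haematologic Grade 3 or 4" event related to AZD2281. Table 6 carries the matching note for haematologic events.

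On recurrence, the text of 4.5.3.6 says that treatment is interrupted again and "on resolution, a further dose reduction made where allowed".

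**The concern.** A second Grade 3-4 event in these rows occurs at the AZD2281 minimum. That is the situation 4.4.6.1 describes, and its instruction is to stop. The tables say to restart AZD2281 at the same amount with less cisplatin. No sentence says which governs.

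For the patient, the question is whether to re-dose an amount of AZD2281 that has just been followed by another Grade 3-4 event attributed to it. For the data, the same clinical event can be recorded as AZD2281 stopped at one site and continued at another, because 5.10.3 collects the action taken for each adverse event. Safety and tolerability are the primary objective, so discontinuations for adverse events would partly reflect which section a site followed. Summarising by initial dose (7.4.3) does not remove this, because the difference arises within one dose group.

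**Working it through.** The plan states no figure to reproduce. The check traces the dose after each event and compares it with the rule in 4.4.6.1.

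**AZD2281 per 21-day cycle** (dose × 2 × days), the same in both rows and both tables:
- Start: 50 × 2 × 5 = 500 mg.
- After event 1: 50 × 2 × 3 = 300 mg, a fall of 1 − 300/500 = 40%. This is the minimum in 4.5.3.6 and Table 8.
- After event 2, following the tables: 50 × 2 × 3 = 300 mg, a change of 0%.
- After event 2, following 4.4.6.1 literally: 0 mg.

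**Cisplatin at event 2, following the tables:**
- Cisplatin 75 row: 1 − 60/75 = 20% lower.
- Cisplatin 60 row: 1 − 50/60 = 16.7% lower.

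**All eight named rows against 4.4.6.1:**

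| Initial dose | AZD2281 after event 1 | After event 2 | Agrees with 4.4.6.1? |
|---|---|---|---|
| 50 mg bid continuous | withdraw | not applicable | Yes |
| 100 mg bid continuous | 50 mg bid (minimum) | withdraw | Yes |
| 200 mg bid continuous | 100 mg bid | 50 mg bid (minimum); third event withdraws | Yes |
| 400 mg bid continuous | 200 mg bid | 100 mg bid; third event withdraws | Yes, minimum not reached |
| 100 mg bid days 1-10 | 100 mg bid days 1-5 | 100 mg bid days 1-3 (100 × 2 × 3 = 600 mg); third event withdraws | Yes, minimum not reached |
| 50 mg bid, under 5 days | 50 mg bid days 1-3, cisplatin 60 | withdraw | Yes |
| 50 mg bid days 1-5, cisplatin 75 | 50 mg bid days 1-3 (minimum) | same AZD2281, cisplatin 60 | **No** |
| 50 mg bid days 1-5, cisplatin 60 | 50 mg bid days 1-3 (minimum) | same AZD2281, cisplatin 50 | **No** |

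Two of eight rows conflict in each table: 2 × 2 = 4 cells.

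**Does the pointer to 4.5.3 reconcile them?** Suppose the lowest reduced dose means the lowest AZD2281 dose in the patient's own row. In these two rows that is still 50 mg bid days 1-3, reached at event 1. The sections agree only if the phrase is taken to include the later cisplatin step, although the sentence names AZD2281 alone.

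**Are DLT decisions touched?** Section 4.1.2 counts DLTs in Cycle 1 only. Table 6 holds the remaining AZD2281 doses of the current cycle after an event. Intermittent dosing restarts in relation to the next cisplatin day (synopsis, Duration of treatment). A second event on re-challenge would therefore ordinarily fall in Cycle 2 or later.

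**The case against.** The best defence is that 4.4.6.1 sends the reader to 4.5.3, where Tables 6 and 7 sit. If the lowest reduced dose means the last step for the initial dose, recurrence there is the third occurrence and every row agrees with the notes. This may well be what the sponsor meant, but it is not what the sentence says, for the reason given in the working.

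The cisplatin step also looks deliberate. Section 4.1.1 allows either agent to be reduced, one at a time, and the recurrence sentence in 4.5.3.6 does not name the agent. The regimen given again is therefore not the one that preceded the event. This stands, and it bears on the remedy. A reader might infer that the four cells are mistakes and should read withdraw; the documents do not show that. Such a change could also remove more patients than 4.4.6.1 requires, since that section speaks of events that recur, while the tables count occurrences and could include a different event.

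The wording is softer in places: the list in 4.4.6.1 opens with may, and the table columns are headed as recommendations. The specific sentence nevertheless says must, so a site that follows the recommendation departs from it.

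One could also confine the 4.4.6.1 rule to events unresolved at 28 days. For non-haematologic events this fails, because 4.5.3.6 withdraws those patients and re-challenge only follows resolution. For haematologic events the support is thinner: 4.5.3.1 removes patients whose neutrophils or platelets have not recovered after 14 days, but does not cover anaemia. The conflict over the AZD2281 minimum does not depend on this argument.

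**Conclusion.** The inconsistency holds, within limits. It concerns only AZD2281-related Grade 3-4 events in the two 50 mg bid days 1-5 rows, and only patients who have a second event. Table 3 plans 4-12 patients for each of the two schedules, and 4.1 makes them contingent on the first intermittent cohort not being tolerated. The protocol gives no event rate, so no share of patients can be stated.

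What changes is the stop-or-restart instruction (0 or 300 mg of AZD2281 per cycle), the recorded action and the discontinuation counts. The occurrence, grade and causality of the event are recorded alike under either reading.

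Two stronger conclusions might be inferred and are not supported. One is that the DLT assessment or MTD is compromised; given the Cycle 1 window, this is not expected. The other is that a stopped patient costs one of the six who must complete four cycles; 4.1.1 and 7.4.5 expand the cohort to ensure six, so such a patient would be made up by further recruitment.

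The conclusion rests on reading the lowest reduced dose as an AZD2281 dose, as the sentence and both stated minimums do. It should be corrected because it is a safety instruction with two answers. No sample size or analysis figure is affected.

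**What to change.** In 4.4.6.1, say that a patient on combination treatment must be discontinued if a Grade 3-4 event recurs at the last step shown for the initial dose in Table 6 or Table 7. Both tables cover combination treatment only, so the existing wording can stay for monotherapy. In 4.5.3.4 and 4.5.3.6, add that in the two 50 mg bid days 1-5 rows AZD2281 restarts unreduced at the second event and only cisplatin is lowered.

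If the sponsor does intend 4.4.6.1 literally, the alternative is to change the four second-event cells to withdrawal, as in the continuous 100 mg bid row. That gives up the cisplatin step and is the sponsor's choice, not the default.

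The cost is one amended sentence and two added ones, or four table cells, in the next amendment. Sample size, visits and analysis are unchanged.

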#### **4.5.3.8 Management of Non-hematologic treatment related adverse events attributable to cisplatin**

Any cisplatin related toxicity, with the exception of ototoxicity, should resolve to  $\leq$  Grade 1 prior to retreatment with cisplatin. Treatment with cisplatin may be continued on Day 1 of each cycle as long as each of the following criteria are met:

- ANC  $>1.5 \times 10^9/L$
- Platelets  $>100 \times 10^9/L$
- Creatinine  $\leq 1.5$  mg/dL
- CrCl  $>50$  mL/min (Creatinine Clearance should be calculated every cycle)
- Neurotoxicity  $\leq$  CTCAE grade 1

#### **Nephrotoxicity**

The major dose-limiting toxicity of cisplatin is cumulative nephrotoxicity. Tubular necrosis of both proximal and distal renal tubules has been noted in 28% to 36% of patients treated with a single dose of  $50 \text{ mg/m}^2$ . It is first noted during the second week after a dose and is manifested by elevations in BUN and creatinine, serum uric acid and/or a decrease in creatinine clearance. Renal toxicity becomes more prolonged and severe with repeated courses of the drug. Renal function must meet the criteria described above before another dose of cisplatin can be given. Nephrotoxicity can be reduced by iv hydration and mannitol diuresis.

If creatinine clearance  $< 50$  mL/min on Day 1 of each cycle;

- hydrate as indicated and hold cisplatin until CrCl is  $>50$  mL/min;
- AZD2281 dose adjustment is not necessary.

## Neurologic toxicity

Although symptoms and signs of cisplatin neuropathy may develop during treatment, symptoms of neuropathy may begin 3 to 8 weeks after the last dose of cisplatin. Cisplatin should be discontinued if CTCAE  $\geq$  grade 3 or functionally important neuropathy develops.

If Grade  $\geq$ 3 neurotoxicity develops:

- Cisplatin should be discontinued
- AZD2281 should be discontinued
- Patient should be removed from study

## Ototoxicity

Ototoxicity has been observed in up to 31% of patients treated with a single dose of cisplatin ( $50 \text{ mg/m}^2$ ) and is manifested by tinnitus and/or hearing loss in the high frequency range (4000 to 8000 Hz.) Decreased ability to hear normal conversational tones may occur occasionally. Ototoxicity can be more severe in children than in adults and more frequent and severe with repeated administration. Hearing loss can be unilateral or bilateral and is usually not reversible. During treatment with cisplatin, it is necessary to monitor hearing at each visit. Audiometric testing should be performed at baseline, at the end of the 2nd, 4th and 6th cycles of cisplatin and as clinically indicated thereafter. A final audiogram should be done at study completion. In the event that cisplatin is permanently discontinued, only the final audiometric test done at study completion is required, unless otherwise clinically indicated.

If Grade  $\geq$ 2 ototoxicity develops:

If a patient had an initial dose level of  $75 \text{ mg/m}^2$  cisplatin, reduce the cisplatin to  $60 \text{ mg/m}^2$ . If the patient had an initial dose level of  $60 \text{ mg/m}^2$  cisplatin, at the investigators discretion, the cisplatin can be reduced to  $50 \text{ mg/m}^2$ .

AZD2281 dose adjustment is not necessary

## Management of hypersensitivity reactions to cisplatin

Reactions, possibly secondary to cisplatin therapy, have been occasionally reported in patients who were previously exposed to cisplatin. Patients who are particularly at risk are those with a prior history or family history of atopy. Facial oedema, wheezing, tachycardia, hypotension and skin rashes of urticarial non-specific maculopapular type can occur within a few minutes of administration. Any reactions should be managed (i.e. by iv adrenaline, corticosteroids or antihistamines) according to local practice. Patients may remain on study after hypersensitivity reactions at the discretion of the investigator providing desensitization protocols are available to the patient.

## Nausea

For CTCAE grade  $\geq 2$  nausea and vomiting attributable to cisplatin and despite the use of optimised anti-emetics, if the patient was on an initial dose level of  $75 \text{ mg/m}^2$  cisplatin, reduce cisplatin to  $60 \text{ mg/m}^2$ . If the patient had an initial dose level of  $60 \text{ mg/m}^2$  cisplatin, at the investigators discretion, the cisplatin can be reduced to  $50 \text{ mg/m}^2$ .

No dose modification is required for AZD2281 (as per [Table 8](#)).

## Other non-haematologic toxicity attributed to cisplatin

Patients with grade 4 non-haematological toxicity attributed to cisplatin will have their cisplatin discontinued unless exception is given by one of the principal investigators and agreed with AstraZeneca. Prior to re-treatment, these non-hematological toxicities must resolve to less than or equal to grade 1. Cisplatin therapy should be delayed for up to 14 days until the toxicity has resolved to  $\leq$  grade 1 or baseline if considered to be treatment related. If the toxicity fails to resolve within a two-week treatment delay, patients will be taken off protocol. For any other CTCAE grade 2 or 3 toxicities, no action should be taken for cisplatin.

**Table 8**                      **Cisplatin and AZD2281 dose adjustments for non-hematologic treatment and Cisplatin-related toxicities.**

Non-Hematologic and Cisplatin Related Toxicities	Management of AZD2281 during cycle	Dose modification of Cisplatin in subsequent cyclesa
Creatinine clearance $< 50 \text{ mL/min}$	No modification	Hydrate as indicated and hold cisplatin until CrCl is $>50 \text{ mL/min}$ , administer cisplatin with a dose reduction to $60 \text{ mg/m}^2$
Grade $\geq 2$ ototoxicity	No modification	Reduce cisplatin to $60 \text{ mg/m}^2$
Grade $\geq 3$ neurotoxicity	Discontinue treatment; remove from study	Discontinue treatment; remove from study
Grade $\geq 2$ nausea and vomiting despite the use of optimised anti-emetics	No modification	Reduce cisplatin to $60 \text{ mg/m}^2$

**Table 8**                      **Cisplatin and AZD2281 dose adjustments for non-hematologic treatment and Cisplatin-related toxicities.**

Non-Hematologic and Cisplatin Related Toxicities	Management of AZD2281 during cycle	Dose modification of Cisplatin in subsequent cyclesa
Other clinically significant grade $\geq 3$ toxicities	Hold up to 28 days until recovery to $\leq$ grade 1 or baseline if considered possibly related; reduce dose as per Table 7. After resumption, if toxicity returns interrupt. If toxicity does not recover to $\leq$ grade 1, discontinue AZD2281. The minimum dose of AZD2281 is 50 mg bid days 1-3 of a 21 day cycle for patients treated with intermittent dosing and 50 mg bid for patients treated with continuous dosing.	Hold up to 14 days until recovery to $\leq$ grade 1 or baseline if considered possibly related; may resume at current dose or with dose reduction, to a minimum of 60 mg/m  , per the Investigator’s discretion
Grade 4 non-hematologic toxicities attributable to cisplatin	No change unless cisplatin is discontinued. If cisplatin is discontinued, at the investigators discretion and if treatment criteria are met, dose of AZD2281 can be escalated to 400 mg bid continuously.	Discontinue cisplatin. If the investigator believes that the patient is benefiting from combination therapy then reducing cisplatin to 50 mg/m  and maintaining the dose of AZD2281 may be considered instead of the above after discussion with the Principal Investigator and agreed by AstraZeneca.

a The dose reductions advised in the table relate to patients who had an initial cisplatin dose of 75mg/m^2, for those patients that had their initial cisplatin dose administered at 60 mg/m^2, the dose modification of cisplatin should be a reduction to 50 mg/m^2 per the Investigator’s discretion.

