#### **4.1.2 Dose Limiting Toxicity**

Toxicity will be graded using the NCI Common Terminology Criteria for Adverse Events (NCI CTCAE) Version 3.0. Dose-limiting toxicity (DLT) is defined as the following study drug-related events experienced during Cycle 1:

- Grade 4 thrombocytopenia.
- Grade 4 neutropenia lasting >5 days.
- Febrile neutropenia (ANC <1.0 x10^9/L with fever ≥38.5°C).
- Treatment delay of >2 weeks.

- Other Grade 3 non-haematological toxicities; excluding non-optimally treated nausea, vomiting and diarrhea

Patients with dose-limiting toxicity after cycle 1 who have documented clinical benefit (stable disease or an objective response) may continue to be treated at a reduced dose level if considered clinically appropriate by the investigator.

Any patient in whom a DLT occurs during any cycle will have his or her treatment delayed until toxicity resolves to grade 1 or below.

[figure not shown]

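### Section 4.5.3.8 tells sites to leave cisplatin unchanged for other Grade 2 or 3 toxicity, contradicting the Table 8 hold, the section's own recovery rule and, for a DLT, the delay rule in 4.1.2

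*Protocol*

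**What the plan says.** Section 4.5.3.8 covers non-haematologic toxicity attributable to cisplatin. It opens with a general rule: "Any cisplatin related toxicity, with the exception of ototoxicity, should resolve to" Grade 1 or lower before cisplatin is given again. A Day 1 list follows, introduced by "Treatment with cisplatin may be continued on Day 1 of each cycle as long as each of the following criteria are met"; it names ANC, platelets, creatinine, creatinine clearance and neurotoxicity.

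Separate paragraphs then deal with kidney, nerve and hearing toxicity, hypersensitivity, and nausea and vomiting. The last paragraph, on other non-haematologic toxicity attributed to cisplatin, starts with Grade 4: discontinue unless an exception is agreed, require recovery before retreatment, and delay for up to 14 days. It adds: "If the toxicity fails to resolve within a two-week treatment delay, patients will be taken off protocol". It ends: "For any other CTCAE grade 2 or 3 toxicities, no action should be taken for cisplatin".

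Table 8 follows at once. Its row for other clinically significant toxicity of Grade 3 or higher is separate from the row for Grade 4 toxicity attributable to cisplatin. The cisplatin cell reads "Hold up to 14 days until recovery to" Grade 1 or lower, or baseline, where the event is considered possibly related. The patient then "may resume at current dose or with dose reduction, to a minimum of" 60 mg/m², at the investigator's discretion.

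Section 4.1.2 adds that a patient with a DLT in any cycle "will have his or her treatment delayed until toxicity resolves to grade 1 or below".

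**The concern.** One clinically significant Grade 3 event related to cisplatin gets opposite instructions from adjoining parts of the same section, and no sentence gives either part precedence. This is a safety instruction in a Phase I combination study whose primary objective is safety and tolerability. With about 4 sites (Synopsis), patients in the same cohort could be handled differently for the same event. A site that takes the last sentence of the paragraph literally could give the next cisplatin dose while a related Grade 3 toxicity is still present. The cohort at the chosen dose must also supply 6 evaluable patients who complete four cycles (Section 4.1), so uneven handling after Cycle 1 would enter the data that support that dose.

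**Working it through.** The plan gives no figure to reproduce here. The check sets the rules side by side and then works out the size of the difference.

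**Step 1: which events the sentence reaches.** The paragraph heading restricts it to toxicity attributed to cisplatin. The toxicities with their own paragraphs drop out. What remains is events such as Grade 3 fatigue, myalgia or skin toxicity, all of which Section 2 lists among the Grade 3 events seen with cisplatin 75 mg/m² in the neoadjuvant trial.

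**Step 2: rules side by side.**

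| Rule | Related Grade 2 | Related Grade 3 |
|---|---|---|
| 4.5.3.8, closing sentence | leave cisplatin alone | leave cisplatin alone |
| 4.5.3.8, opening rule | wait for Grade 1 or lower | wait for Grade 1 or lower |
| Table 8, other significant toxicity | not covered | hold up to 14 days |
| 4.1.2, if the event is a DLT | not a DLT by grade | delay to Grade 1 or lower |

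Rules against the closing sentence: Grade 3, two (opening rule and Table 8, if clinically significant), or three if the event is a DLT; Grade 2, one (opening rule).

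**Step 3: could the sentence mean only that no dose reduction is needed?** Neighbouring paragraphs do prescribe reductions; under Nausea, for a patient who started at 60 mg/m², "at the investigators discretion, the cisplatin can be reduced to" 50 mg/m². The sentence does not say it is limited to dose, and the softer meaning would still differ from Table 8, which permits a reduction on resumption:
- from 75 to 60 mg/m²: (75 − 60)/75 = 20%
- from 60 to 50 mg/m² (footnote a): (60 − 50)/60 = 16.7%

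**Step 4: timing.**
- Second dose due on cycle day 1 + 21 = 22.
- End of the longest Table 8 hold: 22 + 14 = 36.
- Study-day numbering, continuous cohorts only, because Visit 2 does not apply to intermittent cohorts: 8 + 21 = 29, and 29 + 14 = 43.

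The two instructions can differ by up to 14 days for that dose.

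**Step 5: DLT count.** Section 4.1.2 already counts a related Grade 3 non-haematological event in Cycle 1 by grade, apart from nausea, vomiting and diarrhoea that were not optimally treated. What is done with cisplatin afterwards does not change that count. A hold that ends within 14 days also does not meet the separate criterion of a delay of more than two weeks.

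**The case against.** The best defence rests on another sentence in the same paragraph, the one that delays cisplatin for up to 14 days until Grade 1 or baseline if the toxicity is treatment related. It closely matches the Table 8 cell. Its relatedness condition would be redundant if it covered only Grade 4 toxicity already attributed to cisplatin, which is normally discontinued and not held. Read as the text version of the Table 8 row, it leaves the closing sentence to cover only events that are unrelated or not clinically significant, and the contradiction goes away. This reading is possible but not well supported: the heading limits the whole paragraph to toxicity attributed to cisplatin, and the recovery sentence just before the delay sentence refers back to Grade 4.

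It is also fair to say that every other rule points towards holding. To dose over a related Grade 3 event, a site would have to pass over both the section's opening rule and the table directly below the sentence. That stands, and it limits the risk.

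A reader might go further and infer that the Day 1 list lets such a patient through, because none of its five items covers another non-haematological event. The documents do not support that: the recovery rule stands immediately before the list and is the gate.

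**Conclusion.** The contradiction is real, and the closing sentence is the outlier. The consequence is inconsistent management across sites and possible cisplatin dosing over an unresolved related Grade 3 event. The size is a difference of up to 14 days in the next dose, plus an optional reduction of 20% or 16.7% if the sentence is taken to concern dose only. For Grade 2 the only conflict is with the opening recovery rule.

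Two stronger conclusions might be drawn, and neither is supported. The protocol does not plainly permit dosing over Grade 3 toxicity; it gives contrary instructions. Nor does the conflict materially distort the Cycle 1 DLT count, since related Grade 3 events mostly count by grade already.

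No frequency can be given: the Grade 3 events listed in Section 2 for the neoadjuvant cisplatin trial come without attribution or persistence to the next dose. The conclusion assumes that the paragraph heading governs its last sentence. This is a wording correction to a safety rule; no effect on the sample size or the analysis has been identified.

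**What to change.** Replace the closing sentence of the paragraph with:

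> *For any other clinically significant grade 3 toxicity considered possibly related, hold cisplatin for up to 14 days until recovery to grade 1 or less, or baseline, and resume at the current or a reduced dose, as per Table 8. For grade 2 or 3 toxicities not covered by Table 8 or by the recovery rule at the start of Section 4.5.3.8, no action is required for cisplatin.*

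This keeps an instruction for Grade 3 events that are unrelated or not clinically significant, and makes clear that a related Grade 2 event stays under the opening rule. It should not be widened into a new 14-day hold for all Grade 2 toxicity. Together with the off-protocol rule in the same paragraph and the DLT criterion for delays of more than two weeks, such a hold could remove a patient, or count a DLT, for a tolerable event.

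The cost is one passage of text in an amendment, with no new visits or data. The downside is an occasional cisplatin delay of up to 14 days, which Table 8 already requires.
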